5.5 Prophylactic and Rescue Medications

Subjects may not use more than 1 of the following medications with possible migraine-prophylactic effects if not otherwise prohibited by the protocol. Doses must be stable **within 3 months (12 weeks) prior to the start of the Observation Period** and throughout the study. Use of more than 1 of the following medications is prohibited within 3 months (12 weeks) prior to the start of the Observation Period and throughout the study.

Prophylactic migraine medications that are permitted during the study include:

- Topiramate, gabapentin
 - Beta blockers (such as: atenolol, bisoprolol, metoprolol, nadolol, nebivolol, pindolol, propranolol, timolol)
 - Tricyclic antidepressants (such as: amitriptyline, nortriptyline, protriptyline)
 - Venlafaxine, desvenlafaxine, duloxetine, milnacipran
 - Flunarizine, verapamil, lomerizine
-

- Lisinopril, candesartan
- Clonidine, guanfacine
- Cyprohepatdine
- Methysergide
- Pizotifen
- Feverfew, magnesium (≥ 600 mg/day), riboflavin (≥ 100 mg/day)
- Botox®

The use of CGRP antagonists (biologic [e.g. Aimovig™, Ajovy™] or small molecule) other than rimegepant is prohibited during the study.

The use of triptan medications is prohibited during the Open-Label, Extension Phase of the study, but is allowed as rescue medication during the Double-blind, Treatment Phase.

During the Double-blind, Treatment Phase, subjects may use their permitted standard of care medication if needed for acute treatment of a migraine and record any medications taken on the appropriate paper diary. Permitted medications include the following rescue medications: triptans, aspirin, ibuprofen, baclofen, acetaminophen up to 1000 mg/day for a maximum of 2 consecutive days at a time (this includes Excedrin Migraine), naprosyn (or any other type of non-steroidal anti-inflammatory (NSAID)), antiemetics (e.g. metoclopramide or promethazine) or muscle relaxants for rescue during the study, with the exception that **triptans are prohibited during the Open-Label Extension Phase**. These are the only medications allowed for rescue. Subjects should continue taking study medication on scheduled dosing days.

If a subject takes a tablet of study drug and experiences a migraine later that day, after dosing with study drug for the day, the subject may take their ***rescue medication*** as described in this section of the protocol. **During the double-blind, treatment phase, subjects are not allowed to take more than one tablet of study medication EVERY OTHER calendar day. During the open-label, extension phase, subjects are required to dose every other day, but may take 1 tablet of rimegepant on non-scheduled dosing days to treat a migraine. Subjects are not allowed to take more than one tablet of study medication per calendar day during the open-label, extension phase.**

Use of standard of care medication during Observation Period and use of rescue medication during the Treatment Phase, Extension Phase, and standard of care medication through to the 8-Week Follow-up Safety Visit will be recorded by the subject on a paper diary and reported to the site.

5.6 Women of Childbearing Potential

Women of childbearing potential (WOCBP) include any female who has experienced menarche and who has not undergone successful surgical sterilization (hysterectomy, bilateral tubal ligation, or bilateral oophorectomy) or is not postmenopausal. Post menopause is defined as:

1. Amenorrhea greater than or equal to 12 consecutive months (48 consecutive weeks) without another cause and a documented serum follicle stimulating hormone (FSH) level > 35mIU/mL at screening) or
2. Woman with irregular menstrual periods and a documented serum follicle stimulating hormone (FSH) level > 35mIU/mL (at screening) or
3. Woman on hormone replacement therapy (HRT) who no longer menstruate

NOTE: FSH level testing is not required for women greater than or equal to 62 years old with amenorrhea of greater than or equal to one year

NOTE: Women on HRT who still menstruate and women with irregular menses should be considered as WOCBP

Women of childbearing potential (WOCBP) and men must be using two acceptable methods of contraception to avoid pregnancy throughout the study and for up to 56 days after the last dose of investigational product in such a manner that risk of pregnancy is minimized. It is required that all WOCBP use two methods of contraception for the duration of the study (i.e. beginning at first treatment to 56 days **after** the last dose of study drug). The two methods should include one barrier method (ex. condom with spermicidal gel, intrauterine devices, cervical cap etc.) and one other method. The other method could include hormonal contraceptives or another barrier method.

WOCBP will complete a pregnancy test as outlined in [Table 1](#) and [Table 2](#). If a WOCBP suspects that she might be pregnant, she should immediately contact the study doctor.

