4.3 Schedule of Assessments

Table 1. Schedule of Assessments – Double-Blind Treatment Phase^{9, 10}

Procedure	Screening Visit	Observation Period ¹⁰ (28 days, + 3 days)	Pre-Randomization Laboratory Visit: must occur within 96 hours of Baseline (Randomization) Visit ¹¹	Baseline (Randomization) Visit (Day 1)	Week 2 (Day 14 +/- 2 days)	Week 4 (Day 28 +3 days)	Weeks 8 (Day 56) and 12 (Day 84) (all visits + 3 days)
Eligibility Assessments							
Informed Consent	X						
	X						
Inclusion/Exclusion Criteria	X			X			
Medical History	X						
Migraine History (signs/symptoms/prior treatment/frequency/intensity)	X						
Rescue Medication paper diary, Concomitant Medication paper diary and Menstrual Period paper log (female subjects) ¹	X	X	X	X	X	X	X
Randomize subject / IWRS ²				X			
Safety Assessments							
Physical Examination	X			X		X	X
Vital Signs / Physical Measurements ³	X			X		X	X

Procedure	Screening Visit	Observation Period¹⁰ (28 days, + 3 days)	Pre-Randomization Laboratory Visit: must occur within 96 hours of Baseline (Randomization) Visit ¹¹	Baseline (Randomization) Visit (Day 1)	Week 2 (Day 14 +/- 2 days)	Week 4 (Day 28 +3 days)	Weeks 8 (Day 56) and 12 (Day 84) (all visits + 3 days)
Clinical Safety Laboratory Testing	X			X		X	X
Liver Function Test (LFTs)	X		X	X	X	X	X
Lipid Panel				X			
ECG	X			X		X	
Urinalysis				X			
Urine Drug Screen for drugs of abuse	X						
FSH, if applicable, to determine WOCBP status	X						
Pregnancy Test	X (urine)		X (serum)	X (urine)		X (urine)	X (urine)
AE, SAE, and Concomitant Procedure assessment ⁴	X		X	X	X	X	X
Sheehan Suicidality Tracking Scale	X			X	X	X	X
Clinical Drug Supplies / Study Supplies							
Dispense Study Medication ⁵				X		X	X
Administer study medication ⁶					X	X	X
Electronic Diary (eDiary) dispensed	X						

Procedure	Screening Visit	Observation Period¹⁰ (28 days, + 3 days)	Pre-Randomization Laboratory Visit: must occur within 96 hours of Baseline (Randomization) Visit ¹¹	Baseline (Randomization) Visit (Day 1)	Week 2 (Day 14 +/- 2 days)	Week 4 (Day 28 +3 days)	Weeks 8 (Day 56) and 12 (Day 84) (all visits + 3 days)
Enter use of study medication in eDiary				X	X	X	X
Return unused study medication to site for compliance check					X	X	X
eDiary returned / reviewed for completeness ⁷		X	X	X	X	X	X
Other Assessments							
Daily report of migraine occurrence and severity reported by subject in eDiary ⁸		X	X	X	X	X	X
Migraine-Specific Quality-of-Life Questionnaire (MSQ) v 2.1				X			X (week 12 only)

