⁸ The electronic subject diary (eDiary) will be dispensed at the Screening Visit, after all Screening Procedures are completed. The subject will be trained on the use of the eDiary. The subject will use the eDiary every day during the Observation Period and Treatment Phase to report migraine occurrence, migraine severity and if the subject treated the migraine.

⁹ Subjects who do not complete the Double-blind, Treatment Phase or do not enter the Open-label, Extension Phase should complete the End of Treatment Visit and 2-Week and 8-Week Follow-up Safety Visits.

¹⁰ While on-study, all visit windows are used for scheduling purposes and all efforts should be made to return subjects to the 28-day schedule if scheduling changes are made at any previous visit(s).

¹¹ The duration between the Pre-Randomization Lab Visit and the Randomization Visit is 4 days. The “+2” days window is included **for scheduling purposes only**. Every effort should be made to collect the Pre-Randomization Lab Visit samples as close to, and within, the 4 days prior to the Randomization Visit as possible. However, for scheduling convenience, this window may be up to 6 days (between the Pre-Randomization Lab Visit and the Randomization Visit).

Table 2. Schedule of Assessments – Open-label Extension Phase Including End of Treatment (EOT)¹⁰ & Follow-up Visits

Procedure	Phone visit to confirm eligibility based on laboratory criteria¹	Week 14 (Day 98 ± 3 days)	Week 16 (Day 112) and 20 (Day 140) (±3 days)	Visits every 4 weeks Week 24 (Day 168) to Week 64 (Day 448) / EOT (±3 days)	2-Week Follow-up Safety Visit (14 days after EOT visit ± 2 days)	8-Week Follow-up Safety Visit (8 weeks (-2 days to +14 days) after EOT visit)
Confirm Week 12 Laboratory Results	X					
Rescue Medication paper diary, Concomitant Medication paper diary and Menstrual Period paper log (female subjects) ²		X	X	X	X ³	X (Concomitant Medication paper diary only) ³
Safety Assessments						
Physical Examinations			X (Week 16 only)	X (Week 24 and 64 / EOT only)		
Vital Signs / Physical Measurements ⁴			X	X	X	
Clinical Safety Laboratory Testing			X (Week 16 only)	X (Week 24, 48, and 64 / EOT only)		
Liver function tests (LFTs)		X	X	X	X	X
Lipid Panel				X (Week 24 and 64 / EOT only)		
ECG			X (Week 16 only)	X (Week 24, 48, and 64 / EOT only)	X	
Urinalysis				X (Week 64 / EOT only)		
Pregnancy Test			X (urine)	X (urine)	X (urine)	X (serum)

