5.2 Inclusion Criteria

1. Signed Written Informed Consent

- a) Written informed consent must be obtained from the subject in accordance with requirements of the study center's institutional review board (IRB) or ethics committee, prior to the initiation of any protocol-required procedures.
- b) Subjects must be able to read.

2. Target Population

Subject has at least 1 year history of migraine (with or without aura) consistent with a diagnosis according to the International Classification of Headache Disorders, 3rd Edition², including the following:

- a) Age of onset of migraines prior to 50 years of age
 - b) Migraine attacks, on average, lasting 4 - 72 hours if untreated
 - c) Per subject report, 4-18 migraine attacks of moderate or severe intensity per month within the last 3 months prior to the Screening Visit (month is defined as 4 weeks for the purpose of this protocol)
 - d) 6 or more migraine days during Observation Period
 - e) Not more than 18 *headache days* during the Observation Period
 - f) Ability to distinguish migraine attacks from tension/cluster headaches
 - g) Subjects on prophylactic migraine medication are permitted to remain on therapy if the dose has been stable for at least 3 months (12 weeks) prior to the Observation Period, and the dose is not expected to change during the course of the study.
 - i. Subjects may remain on one (1) medication with possible migraine-prophylactic effects, excluding CGRP antagonists [biologic or small-molecule], during the double-blind treatment phase.
-

-
- ii. Concomitant use of a CGRP antagonist, such as erenumab or fremanezumab, is prohibited.
 - iii. Subjects who previously discontinued prophylactic migraine medication must have done so at least 90 days prior to the Screening Visit.
- h) Subjects with contraindications for use of triptans may be included provided they meet all other study entry criteria
3. Age and Reproductive Status
- a) Male and female subjects ≥ 18 years
 - b) Women of childbearing potential (WOCBP) and non-sterile men must be using two acceptable methods of contraception to avoid pregnancy throughout the study in such a manner that the risk of pregnancy is minimized. See Section 5.6 for the definition of WOCBP. Males with vasectomy are considered surgically sterile provided the procedure occurred greater than 6 months (24 weeks) prior to study participation.

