6.2.4 Laboratory Assessments

6.2.4.1 Safety Laboratory Testing

Blood and urine samples will be obtained as outlined in [Table 1](#) and [Table 2](#) for clinical laboratory evaluations. A central laboratory vendor will be utilized for this study and a laboratory manual will be provided to each site. **If possible, subjects should be fasting for a minimum of 8 hours before laboratory tests.** However, if a subject is not fasting at a given visit, the blood draw should still be performed, and the non-fasting status should be documented.

1. Clinical safety labs:

Hematology: Hemoglobin, hematocrit, red blood cell count, white blood cell count with differential, and platelets;

Chemistry: Sodium, potassium, chloride, bicarbonate, calcium; glucose, HbA1c, BUN (urea), serum creatinine, uric acid, LDH, total protein, albumin, CPK (with local lab fractionation, if CK result is $> 5.0 \times \text{ULN}$).

eGFR using the estimated MDRD formula (calculated at central lab);

2. **LFTs:** AST, ALT, Alkaline Phosphatase and Bilirubin (Total, Direct, Indirect). Additional tests may be obtained to evaluate laboratory abnormalities and/or adverse events; please refer to the Laboratory manual.
3. **Lipid panel:** Cholesterol, LDL, HDL, triglycerides
4. **Urinalysis:** pH, specific gravity, ketones, nitrites, urobilinogen, leukocyte esterase, protein, glucose, and blood. If blood, protein or leukocytes are positive, reflex to microscopic examination.
5. **Urine Drug Screen:** For drugs of abuse
6. **FSH:** For WOCBP at screening, to determine WOCBP status

Additional tests may be obtained to evaluate laboratory abnormalities and/or adverse events; please refer to the Laboratory Manual.

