6.2.4.2 Pregnancy Testing

WOCBP will complete pregnancy tests (serum and / or urine) at specified study visits, prior to taking study medication, and as outlined in [Table 1](#).

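### Protocol Section 5.6 classes a woman with irregular menses and screening FSH above 35 mIU/mL both as postmenopausal and as of childbearing potential, so her contraception and pregnancy testing depend on which line the site applies

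*Protocol*

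**What the plan says.** Section 5.6 of the protocol defines women of childbearing potential (WOCBP) as those past menarche who are neither surgically sterilized nor postmenopausal. It then gives three alternative routes to postmenopausal status:

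- Item 1: at least 12 months of amenorrhea and FSH above 35 mIU/mL at screening.
- Item 2: "Woman with irregular menstrual periods and a documented serum follicle stimulating hormone (FSH) level > 35mIU/mL (at screening) or".
- Item 3: on hormone replacement therapy (HRT) and no longer menstruating.

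Two NOTES follow. The first waives FSH testing for women aged 62 or older with at least a year of amenorrhea. The second says "Women on HRT who still menstruate and women with irregular menses should be considered as WOCBP".

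The main duties follow from this status. Section 5.6 states "It is required that all WOCBP use two methods of contraception for the duration of the study", and carries the duty on to 56 days after the last dose. Section 6.2.4.2 states "WOCBP will complete pregnancy tests (serum and / or urine) at specified study visits". Inclusion 3c and exclusion 4a are also written for WOCBP only. Inclusion 3b adds no definition of its own: "See Section 5.6 for the definition of WOCBP".

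**The concern.** Item 2 and the second NOTE use the same descriptor, irregular menses, and reach opposite conclusions. Item 2 adds an FSH condition; the NOTE does not mention FSH. A woman with irregular menses and FSH above 35 mIU/mL is therefore postmenopausal under one line and WOCBP under the other.

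What is at stake is fetal exposure and consistent eligibility decisions. Such women can enroll, because the age criterion is 18 or over with no upper limit. FSH is scheduled only at Screening, so nothing later in the schedule revisits the classification. A monitor also cannot say consistently whether a woman not using two methods has breached inclusion 3b: under the NOTE she has, under item 2 she has not.

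**Working it through.** The documents state no total number of tests, so there is no plan figure to reproduce. The check has two parts.

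**1. Does any other text settle which line governs?**

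| Place in protocol | What it contributes | Settles it? |
|---|---|---|
| 5.2, inclusion 3b | Points back to Section 5.6 | No |
| 4.3, Table 1, FSH row | "FSH, if applicable, to determine WOCBP status" | No: item 1 uses the same test |
| 6.2.4.1, item 6 | "For WOCBP at screening, to determine WOCBP status" | No, for the same reason |
| 5.6, second NOTE, HRT half | Women who still menstruate, the complement of item 3 (women who no longer do) | No: it concerns item 3 |
| 5.6, second NOTE, irregular-menses half | Repeats item 2's descriptor without the FSH condition | No: this is the conflict |

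If the NOTE is read as covering only women who fail item 2, its irregular-menses half adds nothing to the definition. If the NOTE is read literally, item 2 has no effect. The text does not choose between the two.

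**2. How much of the schedule turns on the classification?**

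Inputs are the pregnancy-test rows of Tables 1 and 2 in Section 4.3, for a woman who completes Week 64 and both follow-up visits.

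- Before the first dose: Screening (urine), Pre-Randomization (serum), Baseline (urine) = 3
- Double-blind phase: Weeks 4, 8, 12 = 3
- Extension: Weeks 16 and 20 = 2; Weeks 24 to 64 every 4 weeks = (64 − 24)/4 + 1 = 11; together 2 + 11 = 13
- After end of treatment: 2-week (urine) and 8-week (serum) follow-up = 2

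Results:

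- Scheduled in total: 3 + 3 + 13 + 2 = 21
- In the treatment period: 3 + 13 = 16
- After the first dose: 16 + 2 = 18
- Turning on status, at most: 21 − 1 = 20. The Screening test is removed because it is done at the same visit as the FSH draw.

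The two tests that separate 18 from 20 (Pre-Randomization and Baseline) are less certain. Exclusion 4c bars any woman with a positive test before dosing, so a site may run them whatever her status.

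Contraception: 12 + 52 = 64 weeks of treatment, plus 56/7 = 8 weeks, gives about 72 weeks.

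**The case against.** The strongest reply is that the two lines can be reconciled. The NOTE would be a reminder that irregular menses alone do not establish menopause, and item 2 would be the exception once FSH is documented. That reading leaves every numbered item with a function, and it fits drawing FSH to decide status. Redundancy in a reminder is not a contradiction, so an added clause excepting women who meet item 2 would also remove the conflict. This reading is possible, but the site has to supply the missing words. Sites that do not supply them will follow the NOTE as written, and conduct will differ between sites.

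Some protections do apply under either reading. Exclusions 4b and 4c cover all women before dosing. Pregnancy requires discontinuation for any subject (Section 6.5) and is reportable (Section 8.1.4). Menstrual information is reviewed at visits for all female subjects. This limits the harm but does not close the gap: none of these schedules a test after the first dose or requires contraception.

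Three further points stand:

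- The counts describe one hypothetical completer and say nothing about how many women are affected.
- Reclassifying a woman mid-study has consequences beyond added duties. Extension entry requires that she still meet all entry criteria (Section 4.3.3), and no exceptions are granted (Section 5.8).
- The SAP supplied, version 10.0, is dated by its own revision history to after the final database lock. A re-check of enrolled women helps only those still in treatment or follow-up.

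**Conclusion.** The concern holds. Section 5.6 gives two incompatible classifications for the same woman, and no other text ranks them. For one completer, 18 pregnancy tests after the first dose (16 of them in the treatment period), at most 20 of 21 overall, and about 72 weeks of two-method contraception depend on the line applied.

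The figures assume that she completes Week 64 and both follow-up visits, and that a site treating her as postmenopausal runs none of the WOCBP tests once the Screening FSH is known. The number of women concerned is not in the documents and no estimate is offered. This is a safety and eligibility inconsistency that should be corrected; it does not touch the primary analysis or power.

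**What to change.** Delete item 2 from the definition of post menopause. The second NOTE then governs, any woman with irregular menses is WOCBP, and the Screening FSH serves item 1 only. Deletion is preferable to adding an exception to the NOTE because it takes the more protective of the two rules already written.

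Ask sites to identify any woman still in the study who was classed as postmenopausal under item 2, using the Screening FSH and menstrual log already collected. Apply the WOCBP contraception and testing rules to her from then on. If no subject remains in treatment or follow-up, this step falls away and the deletion matters only where the protocol text is reused.

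The cost is a one-line amendment and a site memo, with no new procedure. Section 11 requires IRB/IEC approval before the change is implemented, and consent is renewed if the change is judged to affect a subject's involvement. The women concerned take on contraception and testing duties, and one who declines them could be refused the extension.

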5.7 Other Restrictions and Precautions (if applicable)

Not Applicable

5.8 Deviation from Inclusion/Exclusion Criteria and Study Procedures

Any significant event that does not comply with the inclusion / exclusion criteria, study conduct, or study procedures will be documented as a deviation. Deviations will be documented and reported through the clinical monitoring of the trial. Deviations will be reported to the IRB/EC at the frequency required by your IRB/EC. There will be no protocol exceptions granted by the Sponsor for Inclusion/Exclusion criteria.

6 STUDY CONDUCT AND DESCRIPTION OF STUDY PROCEDURES

6.1 Study Materials

The following study materials will be provided at the study start:

- Investigator File/Regulatory Binder
- Pharmacy Binder
- Drug Accountability Logs
- Sample source documents, where applicable
- Investigator Brochure
- Interactive Web-based Response System (IWRS)
- Electronic Case Report Form (eCRF) instructions
- Electronic Diary: hand held electronic device (1 will be given to each subject)
- Instructions for the eDiary device and access to the portal
- Paper diary to record standard of care migraine medications and rescue medications
- Paper diary to record menstrual period information (female subjects)
- Laboratory Kits and Laboratory Manual
- ECG Machine and Instructions
- Serious Adverse Event (SAE) forms
- Pregnancy Surveillance Forms
- Sheehan Suicidality Tracking Scale (S-STS) forms
- MIDAS forms
- MSQ v 2.1 forms

All sites will use an Electronic Data Capture (EDC) tool to submit study data to the CRO. Electronic Case Report Forms (eCRFs) will be prepared for all data collection fields including Serious Adverse Events (SAE) Reporting. SAE data (including queries) will be submitted to the CRO using eCRFs.

The eDiary will be used daily to record all study medication dosing, rescue medication dosing occurrences (i.e., with triptans, ergotamine, or other), select subject-rated scales, and migraine occurrence, characteristics, and severity. Any assessment completed by the subject in the eDiary will be transferred from the site/subject to the vendor and from the vendor to the CRO and Sponsor. No additional source documents are required for scales and assessments completed by the subject on the eDiary.

Safety laboratory, plasma, and serum instructions for all specimens collected will be provided by a designated central laboratory. ECG equipment, supplies, instructions and training materials will be supplied by a centralized ECG vendor.

